- b. The VBA site with fact sheets about the different types of benefits available to Veterans. The topics covered in these fact sheets are: General Benefit Information, Veterans with Service-Connected Disabilities, Veterans with Limited Income, Education and Training for Veterans, Home Loans, Dependents and Survivors' Benefits, Burial and Memorial Benefits, and Insurance.
- c. The VBA websites for the local C&P office where issues pertaining to an individual Veteran's specific application are addressed. The site includes phone numbers to call with questions, e-mail contacts and directions to the VBA office.

3. Role of Therapists in Control Condition: The therapists in the control condition will differ from the Benefits Counseling therapist as shown in the table below

Control Therapist	Benefits Counseling Therapist
Initiate calls to Veterans at weeks 1 and 2	Initiate calls to Veteran at weeks 1 and 2 and around time of Module Three (or thereafter)
Up to three therapy calls of up to 30 minutes each	Up to three therapy calls of up to 30 minutes each
Convey information about Veterans Benefits	Convey information about Veterans Benefits AND vocational issues
Offer to elaborate on information on control websites	Inquiry about modules on Benefits Counseling website. Follow-up inquiries about domains covered on site.

Justification of Sample Size

We estimate that 190 Veterans will be enrolled and complete baseline assessments; 130 will log-in to the randomization site and be assigned to a treatment condition; 104 (52 per condition) will complete at least one follow-up assessment.

Precision Analysis

Consistent with the purpose of a pilot study, the sample size was selected to

estimate the standardized effect of treatment with reasonable precision, rather than to power for a statistically significant effect [50]; A **sample size of 52 per treatment condition** permits estimation of an expected standardized difference in slopes of hours worked between Benefits Counseling and control groups (e.g., (slopeBC-slopeCON)/SDslope) of $\delta=.40$ with a 95% confidence interval of (.01, .79). This effect would reflect an average 6% increase in baseline number of hours worked per month, or a total increase of 43% by month 6. Assuming an average baseline event rate of 40 hours/28 days and no change in the control group, this effect is equivalent to approximately 17 additional hours (approximately 2 days) of work per month by month 6.

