- i. Treatment engagement: This will be measured as number of days logging onto the website, number of modules completed, number of minutes spent in telephone calls with the Counselor.
- ii. Treatment satisfaction will be assessed using mean score on subscales of the Likert-scaled Satisfaction questionnaire (with reverse scoring). Satisfaction with discrete elements of the websites will be considered as separate items.
- iii. Number of weeks attending any VA substance abuse and/or mental health treatment will be derived from the service use data.

2. Approach to Missing Data: For analyses involving HLM, maximum likelihood estimation techniques permit missing data on the dependent variable. Valid parameters are estimated from all available data from all cases under the assumption that data are missing at random. To improve the plausibility of the missing-at-random assumption, we may include missing data correlates in the model. For normal models (ANOVA, Regression) requiring complete data, if data are not missing completely at random (MCAR), we will use NORM software to multiply impute missing values. We will first determine whether data are MCAR using Little’s test [75]. If data are not MCAR, we will characterize study drop-outs in terms of differences in mean scores on relevant variables. Variables determined to be related to missingness or to the incomplete variables (missing data correlates) will be included in models to improve estimation [76]. In specifying the imputation model, we will follow guidelines of Rubin [77], Schafer [78, 79] and Collins et al. [76], including all variables that will be included in the analytical models,

as well as all variables that are associated with the variable(s) with missing values, and with missingness itself. We will combine parameter estimates and estimate standard errors according to Rubin's rules [80]. To determine what observed variables are associated with missingness on a given variable, we will create dichotomous "missingness" indicators (missing or not missing; 1/0) and estimate logistic regression models. Variables that significantly predict missingness will be included in the imputation model.

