3. Evaluation of Treatment Effects: For baseline values potentially related to outcome, evaluation of comparability of the two treatment groups will be conducted using chi-square tests for categorical variables and t-tests for continuous variables. If an unexpected difference is found and is related to the outcome, the potentially significant confounding variable will be added to the primary outcome analysis as a covariate.

The principal strategy for assessing the efficacy of the study treatment will be random effects regression, which will be used to determine the differences in slopes of outcomes between Veterans assigned to Benefits Counseling compared to Control. The model will include covariates described in the Introduction Section, time measured in weeks, and the contrasts of Benefits Counseling versus Control. A linear effect of time on outcome variables is being hypothesized but ancillary analyses will be conducted to determine if the effect of Benefits Counseling treatment is better explained by a quadratic function (as described in the Introduction section of this grant). Models will be specified to accommodate the observed distributions of outcomes (e.g., Poisson, normal, Bernoulli) and theory, model estimates, and fit indices will inform the specification of effects as fixed or random, and the structure of the variance-covariance matrix.

Our principal data analyses will be conducted on all randomized Veterans. We will attempt to follow all participants who are randomized for assessments regardless of their retention in treatment. Intention-to-treat analyses will be supplemented by analyses to describe the consistency of findings across different definitions of the sample: e.g., module-completers and treatment completers. Measures of engagement in Benefits Counseling will also be tested for their association with outcomes (number of days using the website, modules completed, minutes on phone with Benefits Counselor).

4. Evaluation of Processes that Might Mediate Treatment Response: This study is not powered for full mediation analyses but will allow for bivariate analyses of the components of mediation. Bivariate analyses will be conducted of the relationship between the slope of each potential mediator and (1) group assignment and (2) slope of hours worked per week. The partial correlation of group assignment with the slope of hours worked per week will be calculated, controlling in turn for each potential mediator's slope.

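### For the few analyses outside the random effects model, imputation depends on Little's test rejecting MCAR, a test that often misses covariate-related dropout at this sample size; the consequences are modest

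*Combined protocol and SAP*

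**What the plan says.** The combined protocol and SAP, Data Analysis, 2. Approach to Missing Data, treats two kinds of model differently.

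- **Hierarchical models (HLM).** These use maximum likelihood, and the plan states that "Valid parameters are estimated from all available data from all cases under the assumption that data are missing at random". No test comes first.
- **Other models.** The rule opens "For normal models (ANOVA, Regression) requiring complete data" and continues "if data are not missing completely at random (MCAR), we will use NORM software to multiply impute missing values". The order is explicit: "We will first determine whether data are MCAR using" Little's test. The section then sets out the imputation model, the missing-data correlates and the use of Rubin's rules.

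The section does not say what happens if Little's test does not reject. It gives no significance level and does not list the variables to be tested. The logistic regressions of missingness choose variables for the imputation model; they are not described as a second route to imputation.

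Under 3. Evaluation of Treatment Effects, "The principal strategy for assessing the efficacy of the study treatment will be random effects regression". Under Justification of Sample Size, "130 will log-in to the randomization site and be assigned to a treatment condition" and "104 (52 per condition) will complete at least one follow-up assessment".

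**The concern.** A non-significant Little's test is weak evidence that data are MCAR when only about 130 people are studied. If it is taken as permission to drop incomplete records, those analyses run on a selected subset and are read as though selection did not matter.

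The condition also protects nothing. Imputation that is valid under MAR is valid under MCAR too, so the only saving is the work of running it. And the section is uneven: it accepts MAR untested for the hierarchical models, but asks for a rejected MCAR test before using a MAR method elsewhere.

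**Working it through.** **Which analyses the rule reaches**

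- Primary and other slope outcomes: random effects regression. Not reached.
- Moderators (Data Analysis, 6): added to the primary outcome model. Not reached.
- Log-ins, modules, therapist minutes, service use and award decision: from the server, contact logs and administrative records. Little affected by missed phone assessments.
- Progress through study steps (Data Analysis, 7): predictors come largely from the face-to-face baseline. Little affected.
- Satisfaction forms mailed at weeks 8 and 24, compared by group under Data Analysis, 5: reached.
- Mediator-slope analyses (Data Analysis, 4): reached if each Veteran's slope is computed separately, not if slopes come from the HLM. The plan does not say which.

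**Inputs.** From the plan: 130 randomized and 104 with any follow-up, so 26/130 = 20% have none. Assumed: alpha .05; one complete, standard normal baseline variable in the test; a logistic model for missingness; the 20% figure standing in for missing satisfaction forms, whose return rate is not stated; baseline-outcome correlation ρ = .6 for bias and .4 to .6 for precision.

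**Chance that the test does not reject.** With one complete variable, Little's test compares its mean between Veterans with and without the outcome. Let D be that difference in SD units. The statistic is approximately noncentral chi-square on 1 df, with noncentrality 104 × 26 / 130 × D² = 20.8 D². D follows from the odds ratio by numerical integration, with overall missingness held at 20%.

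| Odds of missing per SD | D | 20.8 D² | Not rejected | Bias in overall mean, .6 × .20 × D |
|---|---|---|---|---|
| 1.35 | .296 | 1.82 | 73% | .036 SD |
| 1.65 | .481 | 4.81 | 41% | .058 SD |
| 2.0 | .644 | 8.63 | 16% | .077 SD |

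Simulation at N = 130 agreed with these figures. The bias formula follows because completers' baseline mean lies .20 × D from the full-sample mean.

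**More variables in the test.** With 104 versus 26 and D = .5 (noncentrality 5.2), non-rejection is 37%, 62% and 72% with 1, 5 and 10 variables, if only one variable carries the difference. A full simulation of Little's test with N = 130, 20% missing at week 4 and about 30% at week 24 (600 runs per setting) gave, for 2 / 5 / 10 baseline variables:

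- D about .3: 88% / 88% / 91%
- D about .5: 58% / 75% / 80%
- D about .8: 15% / 28% / 54%

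**Bias in a group difference.** With the same dropout mechanism in both arms and an additive effect, the shifts in the two arms cancel; simulated bias was at most .005 SD. If missingness depends on the covariate in one arm only, that arm's shift remains, about .03 to .08 SD. The standard error of a difference with 52 per arm is √(2/52) = .196 SD.

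**Precision under MCAR.** Using the baseline variable multiplies the variance of the mean by 1 − .20ρ². That is 1 − .20 × .16 = .968 at ρ = .4 and 1 − .20 × .36 = .928 at ρ = .6, so complete cases forgo about 3 to 7%.

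**The case against.** The strongest reply is that little depends on this rule. A reader might infer that the trial's main result could rest on complete cases. The documents do not support that: the rule is limited to models needing complete data, and the primary outcome is analysed by maximum likelihood without the test. What remains is a satisfaction form and exploratory mediator analyses that the plan itself says lack power for full mediation. This stands, and it sets the scope of the point.

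A reader might also take the .04 to .08 SD as bias in the treatment comparison. It is bias in a single overall mean. The affected analyses mostly compare groups or correlate slopes, and the group difference is essentially unbiased unless dropout works differently in the two arms. The bias figures also average over all data sets; among those where the test does not reject, bias in the mean is smaller, about .02 to .04 SD. A complete-case regression that already contains the variable driving dropout is not biased by it. All of this stands.

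Finally, the plan never writes that complete cases will be used. That is correct. It is the implied reading, because these models need complete data and no other method is named.

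None of this gives a reason to keep the condition, which can only withhold a method that would be valid either way.

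**Conclusion.** The point holds for the normal models outside the HLM and no further. There, imputation depends on a test that, at 130 Veterans and 20% missing, misses weak to moderate covariate-related dropout in roughly 40 to 70% of trials with one variable tested, and generally more often with several. It does better when dependence is strong and few variables are entered. These rates rest on an assumed alpha, variable set and dropout strength, since the plan states none of them.

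The expected harm is modest: a small bias in overall means, close to none in group differences under similar dropout, and a few per cent of variance. It is worth correcting because the correction is cheap, not because the main conclusion is at risk.

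**What to change.** In Data Analysis, 2. Approach to Missing Data, remove the condition. State that normal models with missing values use the multiple imputation already described, or full-information likelihood, with the missing-data correlates, whatever Little's test shows. Keep Little's test as a description of the missing data, and report complete-case results as a sensitivity analysis. In Data Analysis, 4, say whether the mediator slopes come from the HLM.

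The cost is about one sentence of text in each place, plus running the imputation routinely. The imputation model, its auxiliary variables and the combining rules are already specified. Nothing changes for paid hours or income, which are analysed as slopes in the random effects model.

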Remotely-Delivered Benefits Counseling for Service
Connection Applicants

NCT02677428

4/9/19

Project Description

1. Principal Investigator

[name]

2. Project Title

Remotely-Delivered Benefits Counseling for Service Connection Applicants

3. Purpose

The purpose of this study is to evaluate the utility of Remotely-Delivered Benefits Counseling in a 24-week clinical trial. This study will evaluate the effectiveness of Benefits Counseling on work and work-related outcomes with Veterans who are applying for service-connection. This study has the following specific aims and hypotheses:

Primary Aim 1: To estimate the effect of Remotely-Delivered Benefits Counseling on the slopes of paid work over time.

Hypothesis: The slopes of hours of paid work over time will differ between the control and Benefits Counseling groups, as evidenced by a significant, positive treatment-by-time interaction effect.

Exploratory Aim One: To estimate the effect of Remotely-Delivered Benefits Counseling on other outcomes.

Hypothesis: The slopes of hours of volunteer work; days attending school, days in vocational rehabilitation settings, days engaged in any one of the work-related activities; and income earned over time will differ between the control and Benefits Counseling groups.

Exploratory Aim Two: To conduct bivariate analyses of two of the components of mediation of Benefits Counseling's effects---correlation with the group assignment and with the outcome:

Hypothesis 2A: Assignment to Benefits Counseling (vs. control) will be associated with one or more of the following: (i) more positive changes in ratings of work's importance, (ii) greater decreases in beliefs that working and service connection are linked, and (iii) more positive changes in number of weeks attending any mental health or vocational counseling.

Hypothesis 2B: Individual slopes in hours worked over time will be associated with one or more of the potential mediators (i, ii, iii) as above in Hypothesis 2A.

4. Background

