2. *Feasibility of Randomizing 130 Veterans*: A review of Compensation examinations conducted at Northampton over a 12 month period showed that 547 were conducted for psychiatric conditions. Of these, 348 were initial examinations, 190 were reviews, and 9 were for other reasons. We are estimating that approximately 60% of the 348 will be working fewer than two days per week and receiving less than 30% service-connection. In a chart review of Compensation examinations conducted at our MIRECC site in Bedford, approximately half (17 out of 38) of Veterans coming for new psychiatric Compensation evaluations were both not working *at all* and less than 30% service-connected. Some Veterans will be excluded for other reasons. Therefore, we estimate that 209 eligible Veterans will be approached in a year, which is enough to randomize 130 over two and a half years of recruitment.

3. Balancing the study groups: Participants will be randomized by the Project Director, with assignment delivered by the website, using an urn randomization procedure [52] that offers the benefits of balancing allocation of important prognostic variables in treatment groups, while still retaining other benefits of random assignment. The factors in the urn will be those potentially related to vocational outcomes in Veterans:

- Self-reported use of an illicit drug and/or risky alcohol use within the past 3 months (as measured by the ASSIST, using standard definitions [53,60,61,62]) within the last 28 days. Opioid use will qualify if the opioids were *not* prescribed to the Veteran.
- Current enrollment in VA psychiatric or substance abuse treatment (yes/no).
- Race (African American –yes/no) has been associated with responses to remotely-delivered behavioral messages [54].

Justification for Why Follow-up Data Collection after Baseline will be Done via Telephone:

Timeline followbacks have been administered by phone for substance abuse evaluation and are highly consistent with face-to- face assessments conducted in the same participants---in fact reports of substance use were numerically higher with the telephone assessment, suggesting a greater likelihood of truthful reporting of embarrassing information by phone [55]. The follow-up assessments are also relatively brief, taking 30 minutes or less per session. Veterans will have already completed these assessments at the face-to-face baseline visit so they will be familiar with them when they are re-administered by phone.

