(i.e. going to the website for randomization vs. not doing so; using the Benefits Counseling website if assigned to it vs. not following the assignment). Potential predictors will be screened for their intercorrelations with each other and redundant measures will be pared or combined. We will then use bivariate analyses (t-test, chi-square) to identify factors that differentiate the groups of interest at a significance level of alpha = .10 or less. Identified factors will be entered into a logistic regression with group as the dependent variable (e.g. randomized vs. not). Factors to be considered include internet-associated factors (ease of internet access, extent of internet use), disability related factors (knowledge of disability process, desire to learn more about it), work-related factors (e.g. distress about not working), and demographic variables (age, gender, race, education status), and conditions that make internet use more difficult (e.g. BSI global severity).

Human Subjects

A. Consent Procedures

1. Recruitment: A waiver of informed consent and HIPAA authorization will be obtained to review the Compensation and Pension materials and charts of Veterans scheduled for Compensation and Pension examinations to identify those who are not more than 30% service-connected for physical conditions and scheduled for examinations for a psychiatric condition. The waiver will allow for the collection of basic demographic information concerning Veterans screened for study participation to determine if Veterans who consent to study participation differ systematically from those who do not.

The recruitment strategy involved identifying Veterans who have submitted requests for mental health Compensation examinations. Potentially eligible Veterans will be Express Mailed a letter from the P.I. explaining the basics of the study and that unless the Veteran opts out, a member of the research team will call to further explain the study. The letter will include a phone

number to call to opt not to receive the research call. No phone calls will be made to Veterans calling to opt out.

At that call, the Research Assistant will explain the study and invite the Veteran for a face-to-face meeting with further screening, informed consent, and baseline assessments. A Waiver of written informed consent will be obtained to screen potential participants over the phone.

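### The stated remedy for baseline imbalance, adding a covariate, does not act on the primary slope contrast unless the covariate also has a product with time

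*Combined protocol and SAP*

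**What the plan says.** Purpose, Primary Aim 1 judges the primary hypothesis by a slope difference, "as evidenced by a significant, positive treatment-by-time interaction effect".

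Three places in the plan bear on which covariates enter that model.

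- **Data Analysis, 3. Evaluation of Treatment Effects.** Baseline variables are compared between arms by chi-square and t-tests. The trigger has two conditions: "If an unexpected difference is found and is related to the outcome". When both are met, the consequence given is that "the potentially significant confounding variable will be added to the primary outcome analysis as a covariate". No covariate-by-time term is mentioned.
- **Same item, standing covariates.** "The model will include covariates described in the Introduction Section, time measured in weeks, and the contrasts of Benefits Counseling versus Control". A later sentence, on the quadratic analysis, locates that Introduction outside this document: "as described in the Introduction section of this grant". Under Balancing the study groups, the urn factors are introduced with "The factors in the urn will be those potentially related to vocational outcomes in Veterans" (substance use, current VA treatment, race). Nothing here says that they enter the model.
- **Data Analysis, 2. Approach to Missing Data.** For the mixed models: "To improve the plausibility of the missing-at-random assumption, we may include missing data correlates in the model". The same paragraph defines such correlates and gives a way to find them, by logistic regression on missingness indicators. That selection step is stated for the imputation model.

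**The concern.** A covariate can affect where a participant starts, how fast the participant changes, or both. Confounding of a slope difference comes from the second. A main effect adjusts the first. So a remedy that consists of adding a covariate may leave the primary estimate where it was.

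At stake is the reading of an adjusted result. A report could state that an imbalance had been adjusted for while the imbalance still shifted the slope difference. That difference is what the Precision Analysis says this pilot was sized to estimate.

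**Working it through.** **1. The plan's own figure.** With 52 per arm and d = 0.40, SE = √(2/52 + 0.40²/(4×52)) = 0.198. The interval is 0.40 ± 1.96×0.198 = 0.012 to 0.788, which matches the stated .01 to .79. The simpler SE, √(2/52) = 0.196, is used below.

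**2. Why a main effect does not act.** Take a random intercept, a random slope, independent errors and all four visits (weeks 0, 4, 12, 24). Each participant's data then reduce to a fitted intercept and a fitted slope. A main-effect covariate enters the intercept equation only. The slope equation still contains just a constant and group, a subset of the regressors in the intercept equation. Generalised least squares then gives the plain difference in mean fitted slopes, whatever the variances. Only a covariate-by-time product enters the slope equation.

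**3. Bias if the slope is not adjusted.** Assumed, not in the documents: a binary factor outside the urn, present in 22/52 versus 12/52, shifting the slope by e = 0.2 or 0.4 SDslope.

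- Bias = e × (22 − 12)/52 = 0.2×0.1923 = 0.038, or 0.4×0.1923 = 0.077.
- Against 0.40: 0.038/0.40 = 10% and 0.077/0.40 = 19%.
- In proportion to the plan's 17 extra hours per month by month 6, that is about 1.6 to 3.3 hours.

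**4. How likely, and what it does to error.** With 34 of 104 carrying the factor and 52 per arm, the hypergeometric chance of a difference of 10 or more in either direction is 0.059 for one such factor under simple randomisation. The mean within-arm variance of the factor is v = (22×30 + 12×40)/(2×52²) = 0.211. Given this imbalance and no true effect, with b the bias, r = b/0.196 (0.196 or 0.392) and s = √(1 − e²v) (0.996 or 0.983), the rejection rate is 1 − Φ((1.96 − r)/s) + Φ((−1.96 − r)/s) = 5.34% or 6.37%. Averaged over all allocations it is 5.00% or 5.01%.

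**5. Simulation, normal mixed model.** True effect zero, e = 0.4, known variances, slope reliability 0.5, 2000 runs per row. The factor's effect on starting level was set to 0 and to 0.5. Missed visits means 65 per arm, 20% with no follow-up and 10% missed at each visit. Mean group-by-time estimate in SDslope:

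| Setting | No covariate | Main effect | Time product |
|---|---|---|---|
| Complete | 0.0738 | 0.0738 | −0.0013 |
| Complete | 0.0752 | 0.0752 | −0.0017 |
| Missed visits | 0.0802 | 0.0797 | 0.0028 |
| Missed visits | 0.0715 | 0.0675 | −0.0078 |

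With complete visits the main effect changed the estimate by at most 3×10⁻¹⁵. With missed visits the largest change in any one run was 0.016. A separate simulation, with a continuous covariate correlated 0.3 or 0.5 with slope, gave single-run changes up to 0.035 and almost none on average.

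**6. Other distributions.** Item 3 also allows Poisson and Bernoulli models, where exact invariance is not expected. In a random-effects Poisson check (e = 0.4, 200 runs per setting) the main effect moved the estimate by 0.0002 to 0.0019 SDslope on average, and by up to 0.046 in one run. The time product moved it by 0.080 to 0.083. That check had at most 16% zeros. The Bedford chart review in the feasibility section found 17 of 38 (45%) both not working at all and under 30% service-connected, so a zero-heavy outcome is untested.

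**The case against.** **The model sentence is shorthand.** It omits group-by-time as well, although the sentence before it and Primary Aim 1 plainly require that term. A reader might infer that the plan commits to main effects only. The text does not establish that. It is silent, and on the other reading no bias arises. This objection stands and is the main reason the point is minor.

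**A list may exist.** A reader might infer that the covariates were never fixed. The documents support less: a pointer to a section of the grant that is not reproduced here.

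**Missing data.** A reader might infer that any variable could be brought in as a missing-data correlate. Item 2 does define these and gives a selection rule. It leaves open only whether the rule governs the mixed model and how the variables enter.

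**Error rate.** A reader might infer that test-triggered selection inflates type I error. Simulated with one cut-off applied to both conditions (assumed .05, .10 or .20), the rule gave 0.7% to 5.4%. Reporting the best of several single-covariate models gave 7.0% to 13.1% with 5 to 10 assumed candidates, but nothing in the plan says anyone would do that.

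**No cut-off.** Item 7 states one for a different analysis ("identify factors that differentiate the groups of interest at a significance level of alpha = .10 or less") and item 3 states none. The example split gives p = 0.037 uncorrected and 0.060 with continuity correction, so an assumed .05 cut-off would turn on an unstated option. This is missing detail and does not carry the point.

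**Limited gain for the urn factors.** The urn tends to balance them. Omitting a balanced factor worth 0.2 to 0.4 SDslope only widens the interval by 0.4% to 1.8%, with slightly conservative error. That stands.

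**A fixed list protects only what is on it.** This also stands, so the list must name variables beyond the urn and a sensitivity analysis must remain for the rest.

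**Conclusion.** The concern holds in a limited form, as a minor point. If covariates enter as main effects only, the plan's adjustment cannot correct its own primary contrast in a normal linear mixed model. This is exact with complete visits and nearly so with missed visits. If time products were intended, the plan needs only to say so.

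The size rests on an assumed non-urn factor, an assumed split and an assumed slope effect. It is conditional on an uncommon imbalance and scales directly with those inputs. Confidence is high in the textual gap and in the algebra for the normal model. It is lower for a count model with many zeros.

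**What to change.** In Data Analysis item 3:

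1. Keep the baseline comparisons as description only.
2. Replace the pointer to the Introduction with a covariate list fixed before unblinding. It should contain the three urn factors and named prognostic baseline variables already collected, for example chosen from the predictors in Data Analysis item 6, such as age, PTSD severity or depression.
3. State that the primary model has time, group and group-by-time and, for each listed covariate, a main effect and a product with time.
4. Keep any covariate prompted by an observed imbalance, also with its time product, as a labelled sensitivity analysis. Report the unadjusted model beside it.
5. In item 2, say whether the missing-data rule governs the mixed model and how those variables enter.

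**Cost.** Wording only, with no new data and no change in sample size. The three urn factors add six parameters. If they carry no information, the standard error of group-by-time rises about 1.5% on average (95th percentile 3.9%; 4000 simulated allocations, normal case, simple allocation, assumed prevalences 40%, 50% and 12%). Each further variable adds to this, roughly 1.5%/3 = 0.5% if it scales evenly.

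Race-by-time will be imprecise. For an assumed 12 of 104 participants the 95% half-width is 1.96×√(1/12 + 1/92) = 0.60 SDslope; for 26 it is 1.96×√(1/26 + 1/78) = 0.44. The 12% African American share in the enrollment section describes Northampton only. Treat the term as a nuisance parameter and do not interpret it.
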